3.2.3.2. SUBJECT DISCONTINUATION CRITERIA

The subject discontinuation criteria are described below:

Efficacy discontinuation criteria:

Any subject with < 20% improvement from baseline (of the respective initial Phase IIb study) in both swollen and tender joint count (SJC and TJC; 66/68 counts) at any of the visits at Week 12, 24, 36, 48, 60, 72, 84 or 96, will discontinue from the trial. The visit at which subjects will meet the efficacy discontinuation criteria, is defined as the Early Termination Visit for these patients. Subjects who have to discontinue study drug but are not withdrawing consent for post-treatment follow-up, should return for the Follow-up Visit, planned 12 weeks after the last study drug administration, according to section 3.4.1.3.

Study drug must also be permanently discontinued if any of the following occurs:

- Serious hypersensitivity reaction.
- Following abnormalities in laboratory test results: ALT and/or AST elevations between > 3 and \leq 5 x ULN (confirmed by repeat testing within 2-4 weeks), ALT or AST elevations > 5 x ULN, absolute neutrophil count < 1×10^9 /L, or a platelet count < 50×10^3 / μ L.
- Diagnosis of or suspicion of a serious infection (requiring parenteral antibiotics and/or hospitalization) or TB.
- Malignancy.
- Pregnancy or pregnancy planned within the study period

- Demyelinating disease.
- The initiation of protocol-prohibited medications (see section [3.3.5](#)).
- CHF class III or IV as defined by the New York Heart Association, unstable angina pectoris, myocardial infarction, cerebrovascular accident.
- In case of interruption of study drug administration for 2 consecutive doses.
- The Investigator or the Sponsor's medical monitor deems it is in the subject's best interest.

Discontinuation of study drug must be considered for subjects who develop a severe study drug injection-site reaction or a severe hypersensitivity reaction.

Subjects who have to discontinue according to these criteria but are not withdrawing consent for post-treatment follow-up should return for the Early Termination Visit planned 2 weeks after the last study drug administration (unless they discontinue during a study visit, in which case that becomes their Early Termination Visit). Subjects should also have a Follow-up Visit planned 12 weeks after the last study drug administration, according to section [3.4.1.3](#).

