3.4.2.11. ACR RESPONSE

ACR responses are presented as the numerical measurement of improvement in multiple disease assessment criteria.

ACR 20/50/70 responses are defined as below:

- $\geq 20/50/70\%$ improvement in tender/painful joint count (68 joints) relative to baseline AND
- $\geq 20/50/70\%$ improvement in swollen joint count (66 joints) relative to baseline AND
- $\geq 20/50/70\%$ improvement in 3 of the following 5 areas relative to baseline:
 - Patient's Assessment of Pain (100 mm-VAS).
 - Patient's Global Assessment of Disease Activity (100 mm-VASPA).
 - Physician's Global Assessment of Disease Activity (100 mm-VASPA).
 - Patient's assessment of physical function as measured by HAQ-DI.
 - CRP.

The ACR-N Index of Improvement [24, 25] is defined as the minimum of the following 3 criteria:

- The percent improvement from baseline in TJC.
- The percent improvement from baseline in SJC.
- The median percent improvement from baseline for the following 5 assessments:
 - Patient's assessment of pain (VAS).
 - Patient's global assessment of disease activity (VASPA).
 - Physician's global assessment of disease activity (VASPA).
 - Patient's assessment of physical function as measured by the HAQ-DI.
 - CRP.

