## 6.2 Other Efficacy Analyses

The sensitivity of results to missing data will be assessed by conducting a sensitivity analysis using LOCF imputed cases. Missing post-baseline values are imputed by the last non-missing preceding post-baseline value. Baseline itself is not imputed.

The sensitivity analysis will be done for the following efficacy endpoints:

- ACR20/50/70
- DAS28(ESR) actual values and changes from baseline
- DAS28(ESR) remission/low disease activity
- DAS28(CRP) actual values and changes from baseline
- DAS28(CRP) < 2.6/low disease activity

A second sensitivity analysis will be done using NRI imputed cases. Missing post-baseline ACR values are imputed with the value corresponding to that of non-responders.

This sensitivity analysis will be done for the following efficacy endpoints:

- ACR20/50/70
- DAS28(ESR) remission/low disease activity
- DAS28(CRP) < 2.6/low disease activity

In addition, for the same efficacy endpoints, a subgroup analysis will be conducted on the observed cases.

The following subgroups will be considered:

- Age category (<65 yrs at baseline, >= 65 yrs at baseline)
- Geographic region
- If any subcategory has less than 10% of the total number of patients then the subgroup analysis will not be produced.

A detailed list of tables can be found in section 13.2.

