- ACR20 response:
  - YES if ALL of the following criteria are fulfilled:
    - % improvement relative to baseline in tender/painful joint count  $\geq 20\%$
    - % improvement relative to baseline in swollen joint count  $\geq 20\%$
    - % improvement relative to baseline  $\geq 20\%$  for at least 3 of the following assessments: patient's assessment of pain, patient's global assessment of disease activity, physician's global assessment of disease activity, HAQ-DI, CRP
  - NO if not all of the above criteria are fulfilled
  - Handling of missing values:
    - if TJC or SJC are missing, ACR response will be missing
    - if any of patient's assessment of pain, patient's global assessment of disease activity, physician's global assessment of disease activity, HAQ-DI or CRP are missing, but at least 3 have a change from baseline  $\geq 20\%$  or at least 3 have a change from baseline  $< 20\%$ , ACR response can be derived, otherwise it will be missing.
- ACR50 response: definition similar to ACR20 response, but using 50% as cut-off
- ACR70 response: definition similar to ACR20 response, but using 70% as cut-off

- ACR-N index of improvement: minimum of the following 3 criteria:
  - % improvement relative to baseline in tender/painful joint count
  - % improvement relative to baseline in swollen joint count
  - Median % improvement relative to baseline of the following assessments: patient's assessment of pain, patient's global assessment of disease activity, physician's global assessment of disease activity, HAQ-DI, CRP
- $DAS28(ESR) = (0.56 \times \sqrt{TJC28}) + (0.28 \times \sqrt{SJC28}) + (0.70 \times \ln[ESR]) + (0.014 \times VASPA)$ , with VASPA measured in mm
- $DAS28(CRP) = (0.56 \times \sqrt{TJC28}) + (0.28 \times \sqrt{SJC28}) + (0.36 \times \ln[CRP + 1]) + (0.014 \times VASPA) + 0.96$ , with VASPA measured in mm and CRP in mg/L
- EULAR response is defined as follows based on the actual value of DAS28 (DAS28) in both ESR and CRP and the change from baseline in DAS28 ( $\Delta DAS28$ ) in both ESR and CRP:
  - Good response:  $\Delta DAS28 > 1.2 \text{ AND } DAS28 \leq 3.2$
  - Moderate response ( $\Delta DAS28 > 1.2 \text{ AND } DAS28 > 3.2$ ) OR ( $0.6 < \Delta DAS28 \leq 1.2 \text{ AND } DAS28 \leq 5.1$ )
  - No response ( $\Delta DAS28 \leq 0.6$ ) OR ( $0.6 < \Delta DAS28 \leq 1.2 \text{ AND } DAS28 > 5.1$ )
  - Pooled category Moderate+Good will be shown as well.

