- Disease activity is defined as follows based on the actual value of DAS28(ESR):
  - Remission:  $DAS28(ESR) < 2.6$
  - Low disease activity:  $2.6 \leq DAS28(ESR) \leq 3.2$
  - Moderate disease activity:  $3.2 < DAS28(ESR) \leq 5.1$
  - High disease activity:  $DAS28(ESR) > 5.1$
  - Pooled category Remission + Low disease activity will be shown as well
- Disease activity is defined as follows based on the actual value of DAS28(CRP):
  - $DAS28(CRP) < 2.6$
  - Low disease activity:  $2.6 \leq DAS28(CRP) \leq 3.2$
  - Moderate disease activity:  $3.2 < DAS28(CRP) \leq 5.1$
  - High disease activity:  $DAS28(CRP) > 5.1$
  - Pooled category  $DAS28(CRP) < 2.6$  + Low disease activity will be shown as well
- Boolean remission is defined as follows:
  - Yes:  $TJC28 \leq 1 \text{ AND } SJC28 \leq 1 \text{ AND } VASPA \leq 1 \text{ cm AND } CRP \leq 1 \text{ mg/dL}$
  - No: else
- Clinically meaningful improvement in HAQ-DI (clinically meaningful improvement from baseline – absolute change) is defined as follows:
  - Yes:  $\Delta HAQDI \geq 0.25$
  - No:  $\Delta HAQDI < 0.25$

- Normal physical function based on HAQ-DI is defined as follows:
  - Yes:  $HAQDI \leq 0.5$
  - No:  $HAQDI > 0.5$
- CDAI score = TJC28 + SJC28 + VASPA (cm) + VASPHA (cm)
- CDAI classification:
  - Remission:  $CDAI \leq 2.8$
  - Low disease activity:  $2.8 < CDAI \leq 10$
  - Moderate disease activity:  $10 < CDAI \leq 22$
  - High disease activity:  $22 < CDAI$
  - Pooled category Remission+Low disease activity will be shown as well
- SDAI score = TJC28 + SJC28 + VASPA (cm) + VASPHA (cm) + CRP (mg/dL)
- SDAI classification:
  - Remission:  $SDAI \leq 3.3$
  - Low disease activity:  $3.3 < SDAI \leq 11$
  - Moderate disease activity:  $11 < SDAI \leq 26$
  - High disease activity:  $26 < SDAI$
  - Pooled category Remission+Low disease activity will be shown as well
- Maintained remission at Week x: remission at Week x and all consecutive time points.

MTX and corticosteroid dose related endpoints will be derived as follows:

- MTX dose decrease from baseline at W0, W48 and W104:
  - Yes: daily dose at Week 0/ Week 48 / Week 104 visit < baseline dose
  - No: else
- Discontinuation of MTX dose at W0, W48 and W104:
  - Yes: daily dose at Week 0/ Week 48 / Week 104 visit = 0
  - No: else
- Change from baseline of MTX dose at Week 0/ Week 48 / Week 104
- Change from baseline of corticosteroid dose at Week 0/ Week 48 / Week 104

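### The ACR missing-data rule returns missing at visits where an observed joint count has already ruled out a response

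*SAP*

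**What the plan says.** SAP 12.3 defines ACR20 response by three conditions that must all hold: at least 20% improvement in tender joint count (TJC), the same in swollen joint count (SJC), and the same in at least three of five items (patient pain, patient global, physician global, HAQ-DI, CRP). Otherwise the result is "NO if not all of the above criteria are fulfilled". Protocol 3.4.2.11 has the same structure, with the conditions joined by AND: "improvement in tender/painful joint count (68 joints) relative to baseline AND". ACR50 is a "definition similar to ACR20 response, but using 50% as cut-off", and ACR70 follows the same pattern with 70%.

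Two missing-value rules follow in SAP 12.3:
- For the joint counts: "if TJC or SJC are missing, ACR response will be missing".
- For the five items: if any is missing but at least three reach the cut-off or at least three fall short of it, "ACR response can be derived, otherwise it will be missing".

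Neither rule mentions a joint count that is observed and below the cut-off.

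The main efficacy analysis uses observed cases (SAP 6.1), and missing values are left out of the denominator (SAP 4.3.1). SAP 6.2 adds three analyses of ACR20/50/70:
- an LOCF analysis, in which "Missing post-baseline values are imputed by the last non-missing preceding post-baseline value"
- an analysis that sets missing ACR values to non-response (NRI)
- observed-case subgroup tables by age category and region.

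**The concern.** With a conjunction, one observed failure settles the answer. If TJC has improved by only 10%, no pattern of the five items can produce an ACR20 response. The five-item rule nevertheless returns missing when an item is absent and the remaining items are split. The specific missing-value rule therefore conflicts with the definition just above it in the same section.

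The visits lost are not a random subset. Each is a documented non-response, and the observed-case denominator then excludes it. The error runs one way, in the main analysis and in the subgroup tables, for all three ACR thresholds.

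There is a second, conditional consequence. Protocol 3.2.3.2 withdraws "Any subject with < 20% improvement from baseline (of the respective initial Phase IIb study) in both swollen and tender joint count" at the 12-weekly visits from Week 12 to Week 96. At such a visit ACR20 is certainly NO. If the rule turns that NO into missing, and LOCF is applied to the derived response, an earlier ACR response could be carried forward to Week 104 over a documented failure.

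**Working it through.** The plan states no figure on this point: there is no power calculation and no expected rate of missing items. There is therefore nothing to reproduce, and the check is of the rule itself.

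**Step 1: one worked visit.** TJC improvement 10% (fail), SJC 40% (pass), CRP missing, two items pass and two fail. By the definition ACR20 is NO. Under the five-item rule there are neither three passes nor three failures, so ACR20 is missing.

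**Step 2: all patterns.** Code each component as pass, fail or missing, and keep the patterns with both joint counts observed and at least one failed. There are 3 joint-count patterns × 3^5 = 243 item patterns = 729. By the definition all 729 are NO. The SAP rule returns missing when items are undetermined. Per joint-count pattern:
- 1 item missing, 2–2 split: 5 × 6 = 30
- 2 missing, the other three not unanimous: 10 × 6 = 60
- 3 missing: 10 × 4 = 40
- 4 missing: 5 × 2 = 10
- 5 missing: 1

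The sum is 141, and 3 × 141 = 423. So the rule gives missing in 423 of 729 patterns and NO in 306. It never returns missing where the answer is logically YES. These are pattern counts, not patient frequencies.

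**Step 3: when the rule bites.** Assume each item passes independently with probability q between 0.3 and 0.7.
- One item missing: 6q²(1−q)² = 0.26 to 0.375.
- Two missing: 1 − q³ − (1−q)³ = 0.63 to 0.75.
- Three or more missing: 1.

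**Step 4: effect on a rate.** Take an assumed visit with n = 400 and r = 280 responders (70.0%). If k known non-responders are set to missing, observed cases give r/(n−k). LOCF on the derived response gives (r+k)/n if all k had an earlier response, and (r+k/2)/n if half did.

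| k (share of n) | Observed cases | LOCF, all earlier responders | LOCF, half | NRI or corrected rule |
|---|---|---|---|---|
| 4 (1%) | 70.7% | 71.0% | 70.5% | 70.0% |
| 8 (2%) | 71.4% | 72.0% | 71.0% | 70.0% |
| 20 (5%) | 73.7% | 75.0% | 72.5% | 70.0% |

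**Step 5: plausible size.** Simulation under assumptions: seven component improvements are normal with SD 35 points and pairwise correlation 0.6, items are missing independently at random, and both joint counts are present. Bias of the observed-case ACR20 rate under the SAP rule, in percentage points:

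| Missingness per item | True rate 65% | True rate 80% |
|---|---|---|
| 1% | +0.2 | – |
| 2% | +0.4 | +0.3 |
| 5% | +1.1 | +0.8 |
| 10% | +2.2 | +1.6 |

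If only CRP is missing, at 5%, the bias at a true rate of 65% is +0.2. When a failed joint count gives NO, the bias stays within about half a point of zero in all these settings.

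**The case against.** **The size may be negligible.** Independent missingness of 5% per item means 1 − 0.95^5 = 23% of visits lack at least one item, and 10% means 1 − 0.90^5 = 41%. The items are collected at the same visits, so real rates may be much lower. For an assumed 400 subjects at 65%, the 95% confidence half-width is 1.96 × √(0.65 × 0.35/400) = 4.7 points, and the study is descriptive and unpowered. This stands as a limit on the size. It does not make the rule right. Missing items are also foreseeable: HAQ-DI is not computed with fewer than six category scores (SAP 12.3), and percentage change is not calculable from a baseline of 0 (SAP 4.2.1).

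**A programmer may code NO anyway, from the general definition.** Possible, but the specific rule says missing. ACR20 is the endpoint assigned independent programming (SAP 4.4), so two programmers could defensibly disagree.

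**NRI already covers it.** NRI does classify these visits correctly. It is a second sensitivity analysis, however, and leaves the main and subgroup tables unchanged.

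**LOCF.** A reader might infer that LOCF will overwrite known failures with older responses. The documents do not support that as a general statement. SAP 6.2 lists ACR20/50/70 as endpoints but does not say whether components or the derived response are carried forward, and Protocol 3.6.7 speaks only of a variable. Component-level LOCF would keep the failed count. The harm also needs a missing item, a split pattern and an earlier response. In the simulation model, with both counts failed and exactly one item missing, the result is missing in only 21% to 24% of cases.

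**Boolean remission.** A reader might infer that it has the mirror-image error, because anything not meeting the four limits is scored No. That follows Protocol 3.4.2.16, Figure 4. SAP 12.3 does not address missing Boolean components, and no effect has been quantified. It is not part of this point.

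**Conclusion.** The point holds for visits with both joint counts observed, at least one below the cut-off, and an undetermined five-item part. There the SAP rule contradicts the SAP's own definition and discards only known non-responses, so it can only raise the observed-case ACR20/50/70 rates.

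The expected size is small: about +0.2 to +1.1 points at a true rate of 65% with 1% to 5% missingness per item, under the assumed normal model with independent missingness. The documents give no missingness rate, so this is a range and not a forecast. NRI is unaffected. The LOCF effect is conditional on carry-forward of the derived response. The correction is worth making because it is cheap and the current rule is logically wrong, not because the bias is shown to be large.

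**What to change.** In the ACR section of SAP 12.3:
1. Keep the existing rule "if TJC or SJC are missing, ACR response will be missing".
2. Add after it: *If both TJC and SJC are observed and either improvement is below the cut-off (20/50/70%), ACR response = NO, whatever items are missing.*
3. Apply the existing five-item rule only when both joint counts pass.

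The restriction to both counts observed matters. Scoring NO from one failed count while the other is missing would keep failures and drop passes among incomplete records. In the same model at a true rate of 65%, with joint counts independently missing, that wider rule biases the rate by −1.4 points at 5% and −2.9 at 10%. The restricted rule gives 0.0 with 5% joint-count missingness alone, and is no more than 0.2 points low with 5% missing on both items and counts.

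The cost is one SAP sentence and minor programming, with no new data. Reported ACR rates may fall slightly. The Boolean remission definition needs no change on this account.

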3.6.4. EVALUATION OF EFFICACY PARAMETERS

The following efficacy analyses will be performed:

- The proportion of subjects achieving an ACR response of 20, 50 and 70 over time will be summarized.
- ACR-N index of improvement over time will be summarized.
- The DAS28 (using CRP and ESR) score over time will be summarized.

- The proportion of subjects with DAS28 (using CRP and ESR) response over time will be summarized.
- The proportion of subjects with EULAR response over time will be summarized.
- The change from baseline (absolute change) in disease activity over time will be summarized. The following disease activity scores will be used:
 - DAS28 (CRP and ESR)
 - SDAI
 - CDAI

- The proportion of subjects in remission will be over time summarized, as well as the proportion of subjects who maintained remission at consecutive time points.

The following disease remission definitions will be used:

- DAS28 (ESR) < 2.6
- SDAI ≤ 3.3
- CDAI ≤ 2.8
- Boolean: TJC28 ≤ 1, SJC28 ≤ 1, CRP ≤ 1 mg/dL, VASPA ≤ 1 (on a 0-10 scale)
- The change from baseline (absolute change) in HAQ-DI over time will be summarized.
- The proportion of HAQ-DI responders (i.e., those who have a clinically meaningful improvement from baseline of ≥ 0.25 [absolute change] in HAQ-DI) over time will be summarized.
- The proportion of subjects with HAQ-DI ≤ 0.5, defining normal physical function, over time will be summarized.
- The proportion of subjects with HAQ-DI ≤ 0.5 (normal physical function) with or without remission (DAS28, SDAI, CDAI, and Boolean) at Week 24, 48, 72 and 104 will be summarized.
- The changes from baseline (absolute change) in the physical and mental component scores of SF-36 at Week 24, 48, 72 and 104 will be summarized.
- The change from baseline (absolute change) in SF-36 scales at Week 24, 48, 72 and 104 will be summarized.
- The change from baseline (absolute change) in FACIT-Fatigue at Week 24, 48, 72 and 104 will be summarized.
- The duration of morning stiffness at Week 104 will be summarized.

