#### **Efficacy endpoints:**

- American College of Rheumatology (ACR) ACR20, ACR50, and ACR70 response rate over time (Week 0, Week 12, Week 24, Week 36, Week 48, Week 60, Week 72, Week 84, Week 96 and Week 104).
- Actual values in ACR-N index improvement over time (Week 0, Week 12, Week 24, Week 36, Week 48, Week 60, Week 72, Week 84, Week 96 and Week 104).
- Actual values and change from baseline values in Disease Activity Score using 28 joint counts (DAS28) using CRP and ESR, simplified disease activity index (SDAI) and clinical disease activity index (CDAI) over time (Week 0, Week 12, Week 24, Week 36, Week 48, Week 60, Week 72, Week 84, Week 96 and Week 104).
- Disease activity: response rate of remission and response rate of low disease activity (LDA) based on DAS28(ESR), SDAI, CDAI, Boolean (only remission) over time (Week 0, Week 12, Week 24, Week 36, Week 48, Week 60, Week 72, Week 84, Week 96 and Week 104).
- Disease activity: response rate of DAS28(CRP) < 2.6 and response rate of low disease activity (LDA) based on DAS28(CRP) over time (Week 0, Week 12, Week 24, Week 36, Week 48, Week 60, Week 72, Week 84, Week 96 and Week 104).
- Disease activity: rate of maintained remission at consecutive time points based on DAS28(ESR), SDAI, CDAI, Boolean and rate of maintained LDA at consecutive time points based on DAS28(ESR) over time (Week 0, Week 12, Week 24, Week 36, Week 48, Week 60, Week 72, Week 84, Week 96 and Week 104).
- Disease activity: rate of maintained DAS28(CRP) < 2.6 at consecutive time points and rate of maintained LDA at consecutive time points based on DAS28(CRP) over time (Week 0, Week 12, Week 24, Week 36, Week 48, Week 60, Week 72, Week 84, Week 96 and Week 104).

- European league against rheumatism (EULAR) DAS28 response rate (good, moderate, or no response) over time (Week 0, Week 12, Week 24, Week 36, Week 48, Week 60, Week 72, Week 84, Week 96 and Week 104).
- Actual values and change from baseline values in HAQ-DI over time (Week 0, Week 12, Week 24, Week 36, Week 48, Week 60, Week 72, Week 84, Week 96 and Week 104).
- HAQ-DI response rate (i.e., those who have a clinically meaningful improvement from baseline of  $\geq 0.25$  in HAQ-DI) and HAQ-DI normal physical function response rate (i.e., those who have a score of  $\leq 0.5$ ) over time (Week 0, Week 12, Week 24, Week 36, Week 48, Week 60, Week 72, Week 84, Week 96 and Week 104).

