### **4.3 General Methods**

#### **4.3.1 *Calculation of descriptive statistics***

Continuous variables will be summarized using descriptive statistics including the number of non-missing observations (n), the arithmetic mean, the standard deviation (SD) for general characteristics and for PK summaries or standard error (SE) for efficacy, safety and immunogenicity, the median, minimum and maximum.

Descriptive statistics of efficacy will additionally include a 95% confidence interval (CI) of the mean, calculated based on the large sample normal approximation. For changes from

baseline of efficacy parameters, the least squares (LS) mean and 95% CI derived from an ANCOVA model with treatment group as factor and baseline as covariate will be shown.

Descriptive statistics of PK concentrations will additionally include 5% and 95% percentiles, coefficient of variation (CV)% of arithmetic mean, geometric mean and geometric SD.

Descriptive statistics of continuous variables will be presented when  $n \geq 2$ . When  $n=1$ , only sample size (n) and mean are shown.

Categorical variables will be summarized using frequency counts and percentages. For efficacy, a Wilson score 95% CI on the percentage in each treatment group will also be shown. When count data are presented, the percentage will be suppressed when the count is zero. Missing values will not be included in the denominator count when computing percentages. For demographics and baseline disease characteristics a 'missing' row will be included to indicate the number of missing values, without percentages.

For the graphs showing mean values of continuous variables, an SE flag will be shown, while for graphs showing percentages, this will be the Wilson score asymptotic SE on the binomial proportions.

Calculated parameters will not be rounded in the derived datasets. The rounding will be done at the reporting level. Mean, median, 95% CI limits will be presented with one decimal more than data collected. Minimum and maximum will be reported with the same precision as data collected and SD and SE with two decimals more than data collected. Percentages will be tabulated with 1 decimal.

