## 6 EFFICACY

### 6.1 Main Efficacy Analysis

No inferential statistical analyses will be performed. All tables will be presented by treatment group and overall, including treatment groups defined by previous dosing regimen of the parent trial (cfr. section 4.2.2). All analyses will be run on the ITO. The main analysis will be on observed cases (OC).

Continuous efficacy endpoints will be summarized as follows:

- Actual values: descriptive statistics (mean, 95% CI on the mean [normal approximation], SE, median, minimum, and maximum) per endpoint and time point. The baseline value from the parent trial will be included to the summary, if applicable.
- Changes from baseline: baseline adjusted LS means and 95% CI from an ANCOVA model with treatment as factor and baseline as covariate, median, minimum and maximum per endpoint and post-baseline time point.

This will be done for the following parameters: ACR-N, DAS28(CRP), DAS28(ESR), SDAI, CDAI, HAQ-DI, SF-36 physical and mental component scores, FACIT-Fatigue, duration of morning stiffness, patient's assessment of pain (VAS-scale), patient's global assessment of disease activity (VAS-scale), physician's global assessment of disease activity (VAS-scale), CRP, ESR, TJC68, TJC28, SJC68, SJC28, MTX dose, corticosteroids dose. Different types of systemic corticosteroids will be converted to Prednisolone equivalent doses before calculating the cumulative dose of corticosteroids. The cumulative dose will be given in mg/day (Please refer to Appendix 2 section 16.2 for more details).

Categorical efficacy endpoints will be presented using a frequency tabulation of the parameter at each time point, including a Wilson score 95% CI on the percentage of subjects in the category of interest. The baseline value from the parent trial will be included to the summary, if applicable. This will be done for the following parameters: ACR20, ACR50, ACR70, EULAR response (including EULAR good response), DAS28(ESR) low disease activity / remission / maintained remission / maintained low disease activity, DAS28(CRP) low disease activity / DAS(CRP) < 2.6 / maintained DAS(CRP) < 2.6 / maintained low disease activity, SDAI low disease activity / remission / maintained remission, CDAI low disease activity / remission / maintained remission, Boolean remission / maintained remission, HAQ-DI clinically meaningful improvement, HAQ-DI normal physical function, MTX dose reduction rate, MTX discontinuation rate.

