### **Table 14.2.1.2.3: DAS28 Score – Disease activity (ESR)**

Frequency tabulation of the disease activity, based on the DAS28(ESR) score at each time point, including a Wilson score 95% CI on the percentage of subjects achieving LDA/remission, remission and maintained remission.

Population: ITO.

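### SAP 12.3 defines maintained remission by looking forward from Week x, so it repeats plain remission at Week 104 and, on a fixed denominator, cannot fall even while remission is being lost

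*SAP*

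**What the plan says.** Protocol 3.6.4 plans to summarise remission over time, "as well as the proportion of subjects who maintained remission at consecutive time points". It gives no direction, starting visit or denominator. SAP 3.3 lists the "rate of maintained remission at consecutive time points based on DAS28(ESR), SDAI, CDAI, Boolean" among the efficacy endpoints, at Weeks 0, 12, 24, 36, 48, 60, 72, 84, 96 and 104, with parallel entries for DAS28(CRP) < 2.6 and for maintained low disease activity on DAS28. The only operational definition is in SAP 12.3: "Maintained remission at Week x: remission at Week x and all consecutive time points". That section does not define maintained low disease activity.

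The DAS28(ESR) disease activity table (14.2.1.2.3) puts a Wilson interval on the "percentage of subjects achieving LDA/remission, remission and maintained remission" at each time point. The DAS28(CRP), Boolean, CDAI and SDAI tables follow the same pattern, and the maintained row recurs in the DAS28 tables for LOCF, NRI, age and region.

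SAP 6.1 makes observed cases the main analysis, and SAP 4.3.1 adds: "Missing values will not be included in the denominator count when computing percentages". SAP 6.2 sets two sensitivity analyses. For LOCF: "Missing post-baseline values are imputed by the last non-missing preceding post-baseline value". For non-responder imputation: "A second sensitivity analysis will be done using NRI imputed cases". Both include the DAS28 categories, but not SDAI, CDAI or Boolean remission. Nothing says how a subject with missing later visits is classed for maintained remission.

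**The concern.** The study's objective is long-term efficacy, and this is the only planned endpoint on the durability of remission. Under a forward-looking rule, the value at a visit depends on what happens afterwards, and fewer visits remain to be passed as Week x moves on. The row can therefore climb towards Week 104 because the requirement gets easier, with no change in the disease. Its denominator is not limited to subjects who were in remission, so it mixes those who never reached remission with those who lost it. Someone reading the row from left to right could take the rise as growing durability when remission is in fact being lost. Because the efficacy analysis is descriptive throughout, the printed trend is what will be interpreted.

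**Working it through.** **Inputs.** Ten reporting times from SAP 3.3, hence nine intervals; the definition in SAP 12.3; the missing-data rules in SAP 4.3.1, 6.1 and 6.2. The plan states no remission, relapse or dropout rate, and no figure for this endpoint that could be reproduced. Every rate below is an assumption for illustration.

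**Step 1: logic.** Number the visits k = 0 (Week 0) to 9 (Week 104). Let R_k be plain and M_k maintained remission for one subject. The definition gives M_9 = R_9 and M_k = R_k × M_(k+1). So M_k ≤ M_(k+1) for every subject, and the count of maintained subjects cannot fall from one visit to the next. With a fixed denominator the rate cannot fall either. In 20,000 random complete data sets of 30 subjects by 10 visits there were no violations.

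**Step 2: size with complete data.** Suppose a share s of remitters stays in remission per interval and a share e of the others enters it. Plain remission follows p_(k+1) = s·p_k + e·(1 − p_k), and the SAP rate is m_k = p_k × s^(9−k).

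- Flat remission, p = 0.40, s = 0.90: the SAP rate is 0.40 × 0.90^9 = 15.5% at Week 0, 0.40 × 0.90^5 = 23.6% at Week 48 and 40% at Week 104.
- Falling remission, p_0 = 0.60, s = 0.85, e = 0.03: the long-run level is 0.03/0.18 = 0.1667, so p_9 = 0.1667 + 0.4333 × 0.82^9 = 23.9%. The SAP rate goes from 0.60 × 0.85^9 = 13.9% up to 23.9%. Among Week 0 remitters, the share in unbroken remission is 0.85^4 = 52% at Week 48 and 0.85^9 = 23% at Week 104.
- No relapse and no entry, p = 0.40: the rate is 40% at every visit, so a rise is not inevitable.

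**Step 3: missing data.** Simulation, 200,000 subjects per scenario. Scenario A: 50% in remission at Week 0; per interval, relapse 10%, entry 3%, dropout 2% in remitters and 4% in others. Scenario B: 40% at Week 0; relapse 2%, entry 0.5%, dropout 10% in remitters and 1% in others.

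| Scenario and rule | Plain, Week 0 to 104 | SAP maintained, Week 0 to 104 |
|---|---|---|
| A, complete data | 50.1% to 31.0% | 19.5% to 31.0% |
| A, LOCF | 50.1% to 31.5% | 22.1% to 31.5% |
| A, NRI | 50.1% to 24.9% | 16.3% to 24.9% |
| A, observed, later missing ignored | 50.1% to 33.3% | 22.1% to 33.3% |
| A, observed, later missing = failure | 50.1% to 33.3% | 16.3% to 33.3% |
| B, observed, later missing ignored | 39.9% to 20.5% | 35.8% to 20.5% |
| B, observed, later missing = failure | 39.9% to 20.5% | 12.8% to 20.5% |

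The closed form for A at Week 0, 0.50 × 0.90^9 = 19.4%, agrees with the simulated 19.5%. Maintained equals plain remission at Week 104 in every row. In B the direction of the trend reverses with the choice of an unstated rule.

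**Step 4: what can be recovered.** At Week 0, maintained divided by plain is 13.9/60 = 23.2% in the falling example of Step 2, which is 0.85^9, the two-year sustained share. In scenario A with complete data it is 19.5/50.1 = 39%.

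**The case against.** A reader might infer that the rate must rise, or that the plan cannot show loss of response at all. The documents support neither. The rate is level when nobody relapses or enters remission. In the main observed-cases analysis it can fall, because the denominator changes by visit (scenario B). Plain remission sits in the same tables, where a decline would show; the Week 0 ratio gives the two-year sustained share; and per-subject listings hold the visit-level results. Although SAP 6.1 promises line plots for categorical endpoints in general, the figure index plots plain remission and pooled low disease activity/remission only, so no listed curve shows the maintained rate.

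Further points stand. The SAP does not literally say that the rule runs to the end of the study. Sustained remission among all subjects is a legitimate descriptive quantity. The protocol defines no primary or secondary endpoints, the study is not powered and no inference is planned, so no decision depends on this row.

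These points limit the concern without removing it. No estimate or interval is planned for the Week 0 ratio. The gap between the plain and maintained rows at Week x shows loss after Week x, not when Week 0 remitters lost remission. Scenario B needs heavy dropout among remitters, whereas the efficacy discontinuation rule (protocol 3.2.3.2) tends to remove non-remitters. If the sponsor meant something other than the forward reading, the wording still needs correcting.

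**Conclusion.** The point holds as a defect of definition. On the natural reading of SAP 12.3, the maintained row is redundant at Week 104 under every missing-data rule tried. With complete data, LOCF or NRI it can only stay level or rise, so its trend does not show loss and can run opposite to plain remission: 14% up to 24% while plain remission falls from 60% to 24%. Under observed cases the trend also depends on dropout and on a missing-visit rule that is not written. The logical results rest only on the forward reading; the percentages rest on assumed transition and dropout rates. Loss stays indirectly visible and the endpoint is descriptive, so this is a should-fix.

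**What to change.** Before database lock, replace the line in SAP 12.3 with a definition of *maintained remission through Week x*: in remission at the anchor visit and at every scheduled visit up to and including Week x, with subjects in remission at the anchor visit as denominator. Use Week 0 as anchor and repeat with Week 24. The second anchor brings in C201 placebo subjects, who have had no ALX-0061 at Week 0, and others in remission at Week 24 who first reached it in the extension.

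State how an intermittent missing visit and a discontinuation each count under observed cases, LOCF and NRI, and print the denominator at each visit. Apply the same wording to DAS28(CRP) < 2.6 and to maintained low disease activity, which SAP 3.3 and 6.1 list without a definition. If the all-subjects forward version is kept, label it *sustained from Week x to Week 104* and do not present it as a trend over time.

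The cost is SAP wording and reprogramming of one derived flag, with no new data. Denominators will be smaller. On a fixed denominator the new curve cannot rise, by construction, but its fall then measures loss among subjects who had remission to lose.
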